9.3.5 Subgroup analysis

Subgroup analysis will be defined according to the nature of data.

9.3.6 Safety analysis

The safety analysis will be run on the safety population.

Safety analysis will consider AEs, laboratory parameter values, vital signs, physical examination, PS and 12-Lead ECG data.

Safety variables will include treatment emergent AEs/SAEs (TESS), namely any reported AE occurred or worsened after first study drug intake or clinically relevant change in safety laboratory parameters, physical examination, PS, 12-Lead ECG and vital signs.

TESS will be summarized by primary System Organ Class (SOC) and preferred term (PT). For each PT/SOC, the number of TESS, the number of patients with TESS, and the percentage of patients with TESS will be given. TESS will be listed by dose and age group and stratified by severity (both through mild, moderate, and severe scale and NCI-CTCAE grade), relationship to the IMP (related/not related), and for those leading to study discontinuation.

Serious TESSs will be analyzed analogously as TESSs.

AEs/SAEs which are not considered TESS will be included in a separate listing.

Any AE/SAE with a relationship to the IMP other than “not related”, or “unlikely related” will be considered as treatment-related AEs/SAEs (i.e. ADRs/SADRs).

Laboratory parameters, vital signs, physical examination, PS and 12-Lead ECG will be summarized throughout appropriate descriptive statistics by dose and age group.

9.3.7 Data imputations

Overall, the missing value will not be imputed because an observed cases approach will be used.

For AUC sUA calculation the last observation carried forward method (LOCF) will be applied for patients who discontinued the study prematurely and a linear interpolation method will be used to impute the missing data between visits.

[figure not shown]
9.4 PROTOCOL VIOLATIONS AND DATA REVIEW MEETING

Categories of protocol violations will be defined before the lock of the study database and will be integrated in the Statistical Analysis Plan (SAP).

9.5 STATISTICAL ANALYSIS PLAN

The statistical analysis plan (SAP) will be finalized before the database lock of the study. The SAP will describe in detail study endpoints and the statistical analyses performed, including also additional analyses not planned in the protocol. In case of changes of the original primary endpoint or of the original primary analyses will occur during the study, a substantial protocol amendment will be generated.

Minor deviations (e.g. not involving changes in the primary endpoint and analysis) which might occur during the study will be detailed only in the SAP. All statistical analyses not pre-specified and run after database lock will be considered additional/exploratory analyses.

10. DATA QUALITY MANAGEMENT

10.1 DATA COLLECTION

Data collection activities will be carried out under the responsibility of the Sponsor. Patient data will be collected using the data capture systems described in the following sections. Patients will be identified by the patient study identification number (patient ID), assigned at the Screening Visit.

The patient ID will be a number composed of eight-digits CCCSSPPP:

- CCC is the international phone code of the country (with a leading zeros for countries that have a 1 or 2-digits phone code);
- SS is the site number in the country: it will start from 01 for each country and will be ascending;
- PPP is the patient number in the site; it will start from 001 for each site and will be ascending.

Data will be collected, processed, evaluated, reviewed and stored in anonymous form in accordance with applicable data protection regulations.

10.1.1 Case Report Forms

Clinical data collected during the study at sites will be recorded in an (e)CRF using Medidata RAVE which is a validated system. The Sponsor will be responsible to develop the eCRF based on this study protocol and to review and perform the user acceptance test of the eCRF in order to ensure protocol adherence.

The eCRF will be made available to the study personnel by means of the i-Medidata interface which is a validated system. The accounts will be individual and password-protected.

The Investigator or designee will be responsible for entering study data into the eCRF in accordance to the eCRF Completion Guidelines provided by the Sponsor. In order to improve the quality of data collection and cleaning, data shall be entered into the eCRF as closely as possible to the time when they become available and not later than within 5 working days. The eCRF data will not be considered as source data (the definition of the source data can be found in section 10.3).

Investigators will ensure the accuracy, completeness and consistency of data entered signing electronically the eCRF using the personal password.

An audit trail within the system will track all changes made to the data.

10.1.2 IxRS

The IxRS system [REDACTED], provided by [REDACTED] is a validated system used by the site personnel for the patient screening (including assignment of the patient ID), box assignment and

[figure not shown]
patient status change. Site staff will be provided with a personal user name and password to access to IxRS.

An IxRS user manual will be prepared by [REDACTED] and provided to site personnel by CRO.

Some data such as patient ID and visit dates collected through IxRS system could be automatically integrated in eCRF. The integration process will be detailed in a specific integration document.

10.1.3 Patient diary

As per EMA Guideline of August 1st 2013 [39], the acceptability of febuxostat tablets will be assessed in children through a 5-point hedonic scale anchored with the word super bad and super good [40]. Patients will complete a daily diary, they will mark, immediately after drug intake, the icon best representing their experience of the drug intake. Five levels of acceptability will be provided:

The assessment results will be entered in eCRF by the site personnel.

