8.5.3 Treatment compliance

The study treatment will be dispensed at each study visit starting from Visit 1 (Day 1) to Visit 7 (Day 7) at the site by the Investigator. The Investigator will be given the possibility to prolong treatment duration up to 9 days on the basis of the chemotherapy regimen chosen.

The Investigator will be responsible for documenting the dispensation of the IMP to the patient by entering the treatment box number in the source document and in the eCRF when the treatment is administered to in- as well as out-patients. Furthermore, the number of tablets dispensed and any used/unused IMP will be recorded by the Investigator in the study specific drug accountability form, including dates, quantities, batch/serial numbers, expiry dates, and the unique code numbers assigned to the IMP (treatment number) and patients (patient number).

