8.6.1.2 Visit 1, Start of Treatment (Day 1)

Start of Treatment Visit will be performed 2 days prior to the scheduled chemotherapy. During the Start of Treatment Visit, the following procedures will be performed:

Prior to the drug administration:

- record of adverse events and change in concomitant medication;
- re-check of inclusion/exclusion criteria and patient's eligibility confirmation;
- physical examination and vital signs;
- KPS/LPS evaluation;
- blood sampling and urine collection for safety laboratory tests (**NOTE:** safety laboratory tests performed within 24 hours do not need to be repeated at Visit 1, Day 1);
- blood sampling for centralized laboratory test (sUA); whenever possible blood sampling for centralized laboratory test (sUA) will be collected in conjunction with safety laboratory tests to reduce the patient's discomfort of additional venopunctures;
- assessment of LTLS/CTLS;
- allocation of investigational medicinal product (IMP) treatment box as per IxRS assignment.

Study drug administration:

- administration of febuxostat as per age group.

After study drug administration:

- assessment of the age-appropriate formulation acceptability (only for children).

NOTE: Screening Visit and Visit 1 (Day 1) may occur on the same day. Common assessments will be performed only once.

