8.6.5 Assessment of the age-appropriate formulation acceptability

As per EMA guideline of August 1st 2013[39], the acceptability of febuxostat tablets in children will be assessed through a 5-point hedonic scale anchored with the word super bad and super good [40] immediately after drug intake as reported below:

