9.3 STATISTICAL ANALYSIS

9.3.1 Descriptive statistics

[figure not shown]
[figure not shown]
All study variables will be presented by dose and age group, by using the appropriate descriptive statistics according to the variable nature, unless otherwise specified:

[figure not shown]
- Continuous variables: number of non-missing observations, mean, standard deviation, standard error of the mean, minimum, median, maximum.
- Categorical variables: number of non-missing observations and column percentages (N, %).

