1: PRESENCE presence of LTLS in addition to 1 or more of the following significant clinical complications: renal insufficiency, cardiac arrhythmias, sudden death and seizures.

0: ABSENCE absence of LTLS or absence of any significant clinical complications: renal insufficiency, cardiac arrhythmias, sudden death and seizures.

Chi Square test will be used to compare statistically the rate incidence of LTLS and CTLS by dose and age group.

The efficacy analyses will be run on the ITT population and for exploratory reasons on PP-population.

- ***Assessment of the age-appropriate formulation acceptability***

Assessment of the age-appropriate formulation acceptability will be evaluated through a 5-point

hedonic scale anchored with the word super bad and super good and summarized by means of descriptive statistics by febuxostat dose in children. The analysis will be conducted on the safety population.

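### Acceptability in children is rated only after a dose is taken and summarised on observed ratings, so a dose refused outright drops out of the result

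*Combined protocol and SAP*

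**What the plan says.** Section 7.2 lists acceptability of the formulation in children as a secondary objective. The only instrument is a five-level hedonic scale. Section 8.6.5 has it completed "immediately after drug intake as reported below", and section 10.1.3 says of the children that "they will mark, immediately after drug intake, the icon best representing their experience of the drug intake". On Day 1 (section 8.6.1.2) the "assessment of the age-appropriate formulation acceptability (only for children") comes after the study drug has been given.

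Section 9.3.4 has the ratings "summarized by means of descriptive statistics by febuxostat dose in children", on the safety population. Section 9.2 limits that population to patients who received one dose or more. Section 9.3.7 adds: "Overall, the missing value will not be imputed because an observed cases approach will be used". Its one exception is the sUA area under the curve. Section 9.3.1 summarises categorical variables by the count of non-missing values and column percentages.

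Non-intake is touched on only under compliance, in section 8.5.3: "the number of tablets dispensed and any used/unused IMP will be recorded by the Investigator in the study specific drug accountability form". No section links that record to acceptability, and none says how to rate or count a dose that is refused, spat out or partly swallowed.

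**The concern.** Whether a rating exists depends on what is being measured. A child who will not take the tablets gives the clearest evidence against the formulation, yet on the plan's wording that dose yields no mark and is not counted. A child who refuses every dose is not in the safety population at all.

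A child who swallows one of two or three tablets can mark the diary, and that mark then stands alongside marks for complete doses with nothing to tell them apart.

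At stake is how far the reported acceptability can be trusted. The rationale in section 6.1 rests partly on the lack of an age-appropriate oral option. A high share of favourable marks would be read as support for the tablets even if some doses were never swallowed.

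**Working it through.** The plan states no expected acceptability rate, threshold or refusal rate, so there is no figure to reproduce.

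**Inputs from the documents**
- About 24 children per dose cohort (section 8.5.1).
- 7 to 9 daily doses per child (section 8.5.2), so 24 × 7 = 168 to 24 × 9 = 216 scheduled ratings per cohort.
- 2 tablets per dose at 40 mg and 3 at 60 mg (section 8.4.2).

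**Assumed inputs**
- p, the favourable share among rated doses: 75%, with a range of 60% to 90%.
- r, the share of scheduled doses refused and unrated: 0% to 20%.

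**Formula.** Of N scheduled doses, (1 − r)N are rated and p(1 − r)N are favourable. The plan's summary gives p. With unrated doses counted as not acceptable, the share over all scheduled doses is p(1 − r). The overstatement is p − p(1 − r) = p × r.

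| r | Share over all doses, p = 75% | Overstatement, p = 75% | Overstatement, p = 60% to 90% |
|---|---|---|---|
| 0% | 75.0% | 0 points | 0 points |
| 2% | 73.5% | 1.5 points | 1.2 to 1.8 points |
| 5% | 71.25% | 3.75 points | 3.0 to 4.5 points |
| 10% | 67.5% | 7.5 points | 6.0 to 9.0 points |
| 20% | 60.0% | 15.0 points | 12.0 to 18.0 points |

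In doses, r = 5% is 0.05 × 168 = 8.4 to 0.05 × 216 = 10.8 per cohort.

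**Mean score.** On an assumed 1 to 5 coding with unrated doses scored 1, the overstatement is r × (mean − 1). For an observed mean of 3.5 it is 0.05 × 2.5 = 0.125 at r = 5% and 0.10 × 2.5 = 0.25 at r = 10%.

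**Can tablet counts fill the gap?** Only in part. The cards hold 28 or 42 tablets, enough for 14 days (section 8.4.2), so leftovers are expected even when every dose is taken: 28 − 18 = 10 to 28 − 14 = 14 at 40 mg, and 42 − 27 = 15 to 42 − 21 = 21 at 60 mg. A count can show tablets still in the blister. It cannot show that a tablet was put in the mouth and spat out.

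**The case against.** The case against giving this much weight has several sound parts.

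- **Part-taken doses.** A reader might infer that they drop out too. The text does not support that: swallowing one tablet is an intake, and the child can mark the icon. The same may hold for a tablet spat out, since the child is asked about the experience of taking it. Only outright refusal clearly goes unrated.
- **Direction and size.** A reader might infer that acceptability is overstated as a matter of fact, and more so with three tablets than with two. The documents give no refusal rate for either cohort. If no dose is refused, the bias is zero.
- **Dose comparison.** The cohorts are sequential and not randomised, and section 9.3.4 plans description only, without a test or threshold. There is no formal dose comparison to be biased.
- **Chemotherapy.** A reader might infer that ratings before and after chemotherapy are pooled. No section says so. Ratings are collected daily, and the Day 3 list in section 8.6.1.4 puts the rating ahead of the start of chemotherapy.
- **Visibility.** The count of non-missing ratings is reported, so a shortfall would show.
- **Completeness.** The rating-form figure is not shown, some text is redacted, and section 9.5 leaves detail to a SAP finalised before database lock. A rule could exist there.

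These points limit the claim but do not remove it. A lower count of ratings does not say whether a dose was refused, was not given for another reason, or was taken with the diary left blank. The stated default would leave refusals out.

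**Conclusion.** The point holds in a limited form. With ratings made only after intake and summarised on observed cases, a dose refused outright disappears from the acceptability result, and partial intake is not captured as an outcome.

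The overstatement is conditional. It is p × r: nothing at r = 0, 3.75 points at p = 75% and r = 5%, and 7.5 points at p = 75% and r = 10%. These figures rest on assumed values of p and r and on counting an unrated refusal as not acceptable. If refused doses would have been rated like the others, the ratings themselves would not be biased.

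Severity is low. The endpoint is secondary and descriptive, no decision rule depends on it, and the primary PK analysis is not affected. It is still worth correcting, because whether a dose was spat out or part-swallowed cannot be reliably reconstructed afterwards.

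**What to change.** 1. At each dosing visit, record in the eCRF whether the scheduled dose was fully taken, partly taken, or refused/spat out.
2. In section 9.3.4, report these three shares by dose cohort beside the hedonic ratings. Use all scheduled doses as the denominator, including those of any child who refuses every dose.
3. Add a sensitivity summary that places unrated refused doses in the lowest category and keeps every rating a child actually gave. Scoring every incomplete dose as lowest would override children's own marks, so it is not proposed.
4. Show ratings by day, so that those made before chemotherapy starts can be read separately from later ones.

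The cost is one extra eCRF item per dosing visit and a few lines in the SAP. Section 8.5.3 already has the investigator dispensing treatment at the site at each visit through Day 7, so the observation is feasible. The downside is that reported acceptability may be slightly lower.

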10.1.4 Central Laboratory/Examination data

The following Central Laboratories will be used during the study:

- Research Toxicology Center (RTC) - Pomezia, Rome (Italy) for plasma and serum samples logistic management and centralized laboratory test: sUA
- Menarini Ricerche S.p.A. - Pre-Clinical Research Department - Pomezia, Rome (Italy) for Pharmacokinetics analysis: febuxostat plasma concentrations

Central laboratories data will be managed according to internal laboratory SOPs and will be transferred to Menarini Clinical Research department for statistics and pharmacokinetics analyses.

10.1.5 Data capture systems versions and validation documentation

Versions of the data capture systems can change during the study. The Sponsor will maintain a list of the data capture system versions used and the validation documentation of each version. The list and the validation documentation will be provided to the site at the site initiation visit (SIV) and will be updated at any data capture system version change.

10.2 CLINICAL DATA MANAGEMENT

Data Management will be carried out under the responsibility of the Sponsor. eCRF data will be electronically verified through the use of on-line and off-line checks. Discrepancies in the data will be resolved by means of electronic queries. Data will be locked by the data manager when all activities for the trial, including medical revision of the data, are complete and no more entries are expected.

Data from sources other than eCRF will be provided to the data manager on an agreed scheduled basis. The data manager has the responsibility to reconcile data captured in the eCRF, with external data sources. Discrepancies found in the reconciliation of the data, will be addressed by means of queries.

A clear overview of all clinical data management activities will be given in the data management plan.

10.3 SOURCE DATA

Source data are defined as all data in original records and certified copies of original records of clinical findings, observations or other activities in a clinical trial that are necessary for the reconstruction and evaluation of the trial.

Original documents and data records include, but are not limited to hospital/patients' medical records, laboratory notes, ECG records, patients' identification forms, and pharmacy dispensing records. Study sites will also maintain a paper drug accountability forms for the IMP to document dispensed and returned IMP per patient.

Source data should be held available for perusal by the Sponsor representatives for the study or to other authorized persons such as auditors and inspectors of Regulatory Authorities.

Direct access to source data is defined as the permission to examine, analyze, verify and reproduce any records and reports that are important for evaluation of a clinical trial (see also 10.4.1). Any party allowed to direct access to study source data and documents should take all reasonable precautions within the constraints of the applicable regulatory requirements to maintain the confidentiality of patient identities and sponsor proprietary information.

Data should be consistent with the source documents and discrepancies, if any, should be explained in writing. All the original documentation pertinent to the study procedures must be available for review in each patient's record.

10.4 QUALITY CONTROL/QUALITY ASSURANCE

10.4.1 Study Monitoring

This trial will be monitored in accordance with the ICH Note for Guidance on Good Clinical Practice. Monitoring will be carried out under the responsibility of the CRO. The site monitor will perform visits to the trial sites along the study conduct. Facilities, study drug, storage area, eCRF, patient's source data, and all other study documentation will be inspected/reviewed by the site monitor for adherence to

the protocol and Good Clinical Practice. At each site visit, the monitor will review the eCRFs for completion and accuracy. Accuracy will be checked by performing source data verification that is a direct comparison of the entries made onto the eCRFs against the appropriate source documentation. Any resulting discrepancies will be reviewed with the Investigator and his/her staff. The Investigator agrees to allow access to all study related materials needed for the proper review of study conduct and to assist the monitor during the monitoring visits and during the data cleaning process. Monitoring procedures require that 100% of data are source data verified, particularly focusing on informed consents, adherence to inclusion/exclusion criteria, drug accountability, documentation of SAEs and the proper recording of efficacy and safety measurements. All monitoring activities will be described in detail in the study-specific monitoring plan.

10.4.2 Quality Assurance

Independent study audit(s) and/or inspection(s) may take place at any time during or after the trial. The independent audit/inspection can be carried by the Quality Assurance (QA) Department of the CRO, the independent QA Department of Research Toxicology Centre (RTC) S.p.A., or a Competent Authority. At all times, the confidentiality of subject related documents will be maintained.

11. PREMATURE TERMINATION OF THE WHOLE STUDY

The whole trial may be discontinued at the discretion of the Sponsor in the event of any of the following:

- New information leading to unfavorable risk-benefit judgment of the investigational products due to:
 - Occurrence of significantly previously unknown AEs or unexpectedly high intensity or incidence of known AEs.
 - New evidence of unfavorable safety or efficacy findings (from clinical or non-clinical examinations, e.g. toxicology).
- The Sponsors decision that continuation of the trial is unjustifiable for medical or ethical reasons.
- Discontinuation of development of the IMP.

Competent Authorities and IRB/IECs will be informed about the discontinuation of the trial in accordance with applicable regulations.

12. END OF CLINICAL TRIAL AND ARCHIVING

The clinical trial will end with the collection and analysis of study data and the issue of the clinical study report. All essential documents will be archived by the Sponsor according to the relevant SOP.

